7.2 Method of Treatment Assignment

[figure not shown]
In the phase 1b part of the study subjects will be randomized to receive AMG 592 or placebo in a 3:1 ratio via IVRS.

Assignment to the treatment arms will be based on a computer-generated randomization schedule prepared by Amgen before the start of the study. Each randomized subject will receive a single, unique randomization number via IVRS at randomization. The randomization date is to be documented in the subject's medical record as registered in the IVRS.

7.3 Blinding

The phase 1b part of the study is double-blind. Treatment assignment will be blinded to all subjects and site personnel described below.

7.3.1 Site Personnel Access to Individual Treatment Assignments

A subject's treatment assignment is to only be unblinded when knowledge of the treatment is essential for further clinical management of the subject on this study. Unblinding at the study site for any other reason will be considered a protocol deviation. The Amgen Trial Manager must be notified before the blind is broken unless identification of the study treatment is required for a medical emergency in which the knowledge of the specific blinded study treatment will affect the immediate management of the subject's condition. In this case, the Amgen Trial Manager must be notified within 24 hours after breaking the blind. The date and reason that the blind was broken must be recorded in the source documentation and CRF, as applicable.

7.3.2 Access to Individual Subject Treatment Assignments by Amgen or Designees

Phase 1b

The Amgen early development lead will be unblinded and will monitor the study on an ongoing basis. Other Amgen staff and their designees involved in the study will not be blinded, but will be given access to the unblinding or potentially unblinding information only when there is a need to use the information for analysis, discussion and internal decision-making, in particular, when concerning safety issues. Access to treatment assignments and other restricted data are described in Amgen standard documents. Unblinded individuals will ensure the keeping of the blind. Unblinding and potentially unblinding information should not be distributed to the investigators or subjects prior to a study cohort being formally unblinded.

Approved

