After baseline, CRP results as well as PK/PD parameters that could unblind the study will not be reported to investigative sites or other blinded personnel until the study has been unblinded. ESR will be performed locally. The results of the ESR performed after the subject has been randomized must be maintained in a blinded fashion so that it may not be viewed by other staff who perform any study assessments with the subjects.

Approved

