9.2.5 Pharmacokinetic Assessments

All subjects randomized to AMG 592 will have pharmacokinetic samples assessed.

Blood samples will be collected for measurement of serum concentrations of AMG 592 as specified in the Schedule of Activities ([Table 2-1](#), [Table 2-2](#) and [Table 2-3](#)).

Instructions for the collection and handling of biological samples will be provided by the sponsor. The actual date and time (24-hour clock time) of each sample will be recorded.

Drug concentration information that would unblind the study will not be reported to investigative sites or blinded personnel until the study has been unblinded.

Approved

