9.2.8 Antibody Testing Procedures

Blood sample(s) for antibody testing are to be collected according to the timepoints specified in the Schedule of Activities ([Table 2-1](#), [Table 2-2](#) and [Table 2-3](#)) for the measurement of anti-AMG 592 binding antibodies. Samples testing positive for binding antibodies will also be tested for neutralizing antibodies and may be further characterized. Additional blood samples may be obtained to rule out anti-AMG 592 antibodies during the study.

Subjects who test positive for anti-AMG 592 antibodies that cross-react with and neutralize native human IL-2 at the final scheduled study visit will be asked to return for additional follow-up testing. This testing is to occur approximately every 3 months starting from when the site has been notified of the positive result until: (1) IL-2 neutralizing antibodies are no longer detectable; or (2) the subject has been followed for a period of at least 1 year (\pm 4 weeks) post administration of AMG 592. All follow-up results, both positive and negative will be communicated to the sites. This notification is independent of and may be in advance of the time point when the entire study is planned to be unblinded. Refer to [Section 7.3](#) for additional information regarding unblinding. More frequent testing (eg, every month) or testing for a longer period of time may be requested in the event of safety-related concerns. Follow-up testing is not required where it is established that the subject did not receive AMG 592.

Subjects who test positive for binding, non-neutralizing antibodies and have clinical sequelae that are considered potentially related to an anti-AMG 592 antibody response

may also be asked to return for additional follow-up testing. Refer to the Schedule of Activities ([Table 2-1](#) and [Table 2-2](#)), as applicable, for specific timepoints, and the laboratory manual for detailed collection and handling instructions.

[figure not shown]

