- The investigator is obligated to assess the relationship between investigational product, protocol-required therapies, and/or study-mandated procedure and each occurrence of each adverse event/serious adverse event.
- Relatedness means that there are facts or reasons to support a relationship between investigational product and the event.
- The investigator will use clinical judgment to determine the relationship.
- Alternative causes, such as underlying disease(s), concomitant therapy, and other risk factors, as well as the temporal relationship of the event to study treatment administration will be considered and investigated.
- The investigator will also consult the Investigator's Brochure and/or Product Information, for marketed products, in his/her assessment.
- For each adverse event/serious adverse event, the investigator must document in the medical notes that he/she has reviewed the adverse event/serious adverse event and has provided an assessment of causality.
- There may be situations in which a serious adverse event has occurred and the investigator has minimal information to include in the initial report. However, it is very important that the investigator always make an assessment of causality for every event before the initial transmission of the serious adverse event data.
- The investigator may change his/her opinion of causality in light of follow-up information and send a serious adverse event follow-up report with the updated causality assessment.
- The causality assessment is 1 of the criteria used when determining regulatory reporting requirements.

Approved

Follow-up of Adverse Event and Serious Adverse Event

- The investigator is obligated to perform or arrange for the conduct of supplemental measurements and/or evaluations as medically indicated or as requested by Amgen to elucidate the nature and/or causality of the adverse event or serious adverse event as fully as possible. This may include additional laboratory tests or investigations, histopathological examinations, or consultation with other health care professionals.
- If a subject is permanently withdrawn from protocol-required therapies because of a serious adverse event, this information must be submitted to Amgen.
- If a subject dies during participation in the study or during a recognized follow-up period, the investigator will provide Amgen with a copy of any post-mortem findings including histopathology.

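### Does telling sites about antibody results under Protocol 9.2.8 contradict the blinding rule in Protocol 7.3.2?

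*Protocol*

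**What the plan says.** Several parts of the protocol govern when blinded data may reach a site.

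- **Section 7.3.2 (phase 1b)** works by cohort: "Unblinding and potentially unblinding information should not be distributed to the investigators or subjects prior to a study cohort being formally unblinded".
- **Section 9.2.4**, repeated in Appendix 2, works by study. Post-baseline CRP and "PK/PD parameters that could unblind the study will not be reported to investigative sites or other blinded personnel until the study has been unblinded". **Section 9.2.5** does the same for drug levels: "Drug concentration information that would unblind the study will not be reported to investigative sites or blinded personnel until the study has been unblinded".
- **Section 9.2.8** covers subjects whose anti-AMG 592 antibodies cross-react with and neutralize native IL-2 at the final scheduled visit. They are asked back about every 3 months, counted from when the site is notified. "All follow-up results, both positive and negative will be communicated to the sites", and "This notification is independent of and may be in advance of the time point when the entire study is planned to be unblinded". It adds that "Follow-up testing is not required where it is established that the subject did not receive AMG 592", and refers to Section 7.3 for unblinding.
- **Section 7.3.1** allows a subject's assignment to be opened at the site when that is essential to clinical management. "Unblinding at the study site for any other reason will be considered a protocol deviation".

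Neither 7.3.1 nor the phase 1b text of 7.3.2 mentions antibody results.

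**The concern.** Read in sequence, these sections seem to give three release dates: cohort unblinding, study unblinding, and as results arise. The third looks like a breach of the first. Because 9.2.8 exempts subjects known not to have received AMG 592, a call-back points towards active treatment, which makes the notice potentially unblinding. A reader sent from 9.2.8 to Section 7.3 for guidance finds none there.

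The stake would be the primary safety endpoint. Site investigators judge whether an adverse event is related to investigational product, and Appendix 4 says that "The investigator may change his/her opinion of causality in light of follow-up information". SAP 9.6.2 tabulates treatment-related and serious treatment-related events, and SAP 7.2.1 places the primary analysis after all subjects have finished. An investigator who has inferred a subject's arm could therefore alter an attribution before the tables are run.

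**Working it through.** **1. Do the release dates exclude each other?**

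| Source | What is released | Earliest release to site |
|---|---|---|
| 7.3.2 | anything potentially unblinding | cohort formally unblinded |
| 9.2.4, 9.2.5, Appendix 2 | CRP, PK/PD, drug concentration | study unblinded |
| 9.2.8 | antibody result and follow-up results | not tied to unblinding of the *entire* study; no cohort condition, no deadline |

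The first two rows set earliest dates, so waiting for the later one meets both. The third row lifts only the study-level date. A notice sent after the cohort is unblinded but before the entire study is unblinded complies with 7.3.2 and with 9.2.8.

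**2. Is there room between those two dates?** Assume zero enrollment time, with day 1 the first dose in cohort 1. Cohort 1 ends on day 127. Cohorts 2 and 3 start on day 29. Cohort 4 starts on day 57 (after the first dose level review of cohorts 2 and 3) or day 85 (after the second). It ends on day 57 + 126 = 183 or 85 + 126 = 211. The gap is 183 − 127 = 56 days or 211 − 127 = 84 days, that is 8 or 12 weeks. It is longer with real enrollment, or if the study includes phase 2a. So the early-release sentence in 9.2.8 has work to do even under the cohort rule.

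**3. Could a notice come before cohort unblinding?** Yes, if sent promptly. The clearest case is the first half of cohorts 2 and 3. If the second half is dosed after the first review at day 29, then on a first-half subject's day 127 a second-half subject is at day 127 − 29 + 1 = 99 at most, with at least 28 days left. At that minimum only the first notice could be early, since follow-up results come about every 3 months. Slow enrollment or early termination lengthens the gap.

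**4. What would a notice reveal?** It is not the treatment code. If the sponsor applies the exemption first, a called-back subject is on AMG 592 with certainty, against 75% by randomization. Without that check, with *r* the ratio of placebo to active positivity, the probability is 0.75/(0.75 + 0.25*r*): 100% at *r* = 0, 86% at *r* = 0.5 and 75% at *r* = 1. It says little about anyone else: with 6 of 8 on active, learning that one subject is active moves another from 6/8 = 75% to 5/7 = 71%.

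**5. Which data could change?** The trigger is the sample at the final scheduled visit. For a completer the last dose is on day 85, and SAP 5.3 closes the treatment-emergent window no later than 85 + 42 = day 127, the week 18 visit. For an early terminator the safety visit is 6 weeks ± 3 days after the last dose, so the 42-day cap falls within 3 days of it. Essentially only the causality of events that have already begun is exposed. One change moves treatment-related incidence by 1/12 = 8.3 points in cohort 2 or 3, or 1/36 = 2.8 points pooled. The larger step, 1/6 = 16.7 points, belongs to cohorts 1 and 4, which have no second half; the case in step 3 does not arise there.

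**6. How often?** The documents give no antibody rate. Borrowing the 1% and 5% adverse event rates of Protocol 10.1.1 purely as an assumption:

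- at least one positive among 36 on AMG 592: 1 − 0.99³⁶ = 30%, 1 − 0.95³⁶ = 84%
- among the 12 on AMG 592 in the first halves of cohorts 2 and 3: 1 − 0.99¹² = 11%, 1 − 0.95¹² = 46%

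These are chances that any such subject exists. A biased attribution also needs a notice before cohort unblinding, an event whose causality is still unsettled, and a change of mind because of the notice. The documents support no figure for that joint event, which must be rarer.

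**The case for a change.** The best case for acting is that 9.2.8 states no wait for the cohort. Its follow-up clock starts at notification, so a prompt notice is the natural reading, and the subject, whom 7.3.2 also protects, learns of it by being asked back. The rationale for Amendment 3 reports many early dropouts in cohorts 2 and 3, and such subjects reach their final visit well before their cohort ends. Investigators also vote at dose level reviews, and relatedness counts towards the Grade 3 scenario in Table 7-1.

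Part of this stands. The protocol does not say which rule yields when a notice falls due before cohort unblinding, and a cross-reference would be tidier.

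The rest does not carry a change:

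- 9.2.8 announces its own early release and refers to Section 7.3. It reads as a deliberate, specific safety provision, and an exception sentence in 7.3.2 would only restate it.
- 7.3.1 concerns opening the treatment assignment at the site. An antibody result sent by the sponsor does not do that, so no deviation arises from it.
- The Appendix 4 sentence on changing causality goes on to describe sending a serious adverse event follow-up report. It is weak support for wide revision of ordinary events.
- Under Table 7-1 the dose level review itself examines relationship to treatment and may consider unblinding, so a site's attribution does not settle the matter alone.
- Imposing one phase 1b release date throughout would do harm. Sections 9.2.4, 9.2.5 and Appendix 2 also serve phase 2a. Read literally, such wording would end the bar on CRP and PK for phase 2a subjects once phase 1b was unblinded, and CRP is a component of ACR 20, the phase 2a primary endpoint.

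**Conclusion.** No change follows. The cohort and study wordings are compatible, and 9.2.8 can be carried out within 7.3.2. What remains is a missing cross-reference, which the sponsor's staff, who are not blinded in phase 1b, can handle when a notice arises. Exposure is limited to the causality of events already under way in the few subjects notified early, worth 8 points per changed subject in an expanded cohort and 3 points pooled. Phase 1b is descriptive, with no test or formal interim analysis, and the tables of all, serious and fatal events do not use causality. A second set of causality tables would alter no foreseeable conclusion.

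This rests on two assumptions that the documents do not settle: that formal cohort unblinding follows reasonably soon after the cohort's last visit, since no date is given, and that IL-2-neutralizing antibodies at the final visit are uncommon. If they proved common, a prompt notice could unblind several subjects, but still only after their scheduled assessments were complete.

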7.4 Dose Modification

7.4.1 Hepatotoxicity Stopping Rules

Refer to [Appendix 7](#) for details regarding drug-induced liver injury (DILI) guidelines, as specified in the Guidance for Industry Drug-Induced Liver Injury: Premarketing Clinical Evaluation, July 2009.

7.4.2 Dose-cohort Study Escalation/De-escalation and Stopping Rules (Phase 1b)

7.4.2.1 Dose Level Review Meetings

After all evaluable subjects within a cohort have completed the week 4 visit, a DLRM will be held to review data and make dose escalation/de-escalation decisions (see [Appendix 3](#)). **The exception is for cohorts 2 and 3 where an initial DLRM will convene after the first 16 enrolled subjects (8 in each cohort) complete the week 4 visit and a second DLRM will convene after the remaining 16 enrolled subjects (8 in each cohort) complete the week 4 visit.**

7.4.2.2 Dose Cohort Stopping Rules

The following dose cohort stopping rules will be used in the phase 1b part of the study. Dosing will be stopped or modified as shown in [Table 7-1](#).

Approved

Table 7-1. Dose Cohort Stopping Rules

| Scenario | Action |
|--|--|
| 
Occurrence of a CTCAE version 4.03 Grade 3 adverse event deemed related to investigational product in 2 or more subjects within in a single dosing cohort
 | 
Stop dosing and convene DLRM (if event occurs outside the regularly scheduled DLRM)
 
Review adverse event and all relevant safety data for evidence of relationship to treatment and clinical or medical significance
 
Consider unblinding, as appropriate^a
 
Upon majority vote by the DLRM members, one of the following recommendations may be made
 
 • stop enrollment of the cohort (if applicable) • enrollment of the cohort may resume as planned • the cohort may be expanded at the same dose • enrollment of the study may continue at a lower dose 
OR
 
Upon unanimous vote by the DLRM members, 1 of the following recommendations may be made:
 
 • escalation to an intermediate dose (a dose lower than the next planned dose) may take place • escalation to the next planned dose may occur |
| 
Any occurrence of a CTCAE version 4.03 ≥ Grade 4 adverse event
 | 
Stop dosing additional subjects in the cohort and convene DLRM (if the event occurs outside the regularly scheduled DLRM)
 
Review adverse event and all relevant safety data for evidence of relationship to treatment and clinical or medical significance.
 
Consider unblinding to determine relatedness to investigational product^a
 
If the adverse event is determined by majority vote of the DLRM members to be related to the investigational product and clinically or medically significant, no further doses should be administered at this dose and no dose escalation should proceed. Enrollment of the study may continue at a lower dose or a lower dose cohort may be added to the study.
 
Otherwise, upon majority vote of the DLRM members, one of the following recommendations may be made:
 
 • enrollment of the cohort may resume as planned • the cohort may be expanded at the same dose • enrollment of the study may continue at a lower dose or a lower dose cohort may be added to the study |

^a subject's treatment assignment should only be unblinded when knowledge of the treatment is essential for the further management of the subject, or may impact the safety of subjects currently enrolled or of subjects in subsequent cohorts. A decision to stop dosing will not occur without unblinding of the subject's treatment assignment.

Approved

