Additional dosing cohorts may be added **and/or existing cohorts may be expanded** based on emerging data. These cohorts may be used to explore alternate dosing levels and/or dosing schedules or add additional subjects at previously given dose levels. A DLRM is required for escalation to higher doses but not for allocation of additional subjects to doses equivalent to or lower than previously given that have been deemed

Approved

[figure not shown]
tolerable. Additional dose levels will not exceed [REDACTED]
[REDACTED]
[REDACTED]
[REDACTED] For additional details on the DLRM see [Appendix 3](#).

Subjects will be treated for a total of 12 weeks after which they will complete a 6-week follow-up until week 18 for collection of additional safety, PK and PD data as described in the Schedule of Activities ([Table 2-2](#)). For subjects who complete the study at week 18, the visit includes all required safety follow-up data collection. All subjects who terminate the study early (ie, prior to completing the week 18 visit), will complete an Early Termination visit consisting of all assessments included in the week 12 day 85 pre-dose visit. In addition, a safety follow-up visit will occur 6 weeks (\pm 3 days) after the last dose of investigational product to collect all required safety data including adverse events, serious adverse events, disease related events, concomitant therapies, safety labs/assessments, anti-AMG 592 antibody, and urine pregnancy test.

[REDACTED]
[REDACTED]
[REDACTED]
[REDACTED] The phase 2a part of the study will commence after a RP2D is identified in the phase 1b part of the study. [REDACTED]
[REDACTED]
[REDACTED]
[REDACTED]
[REDACTED]
[REDACTED]

[REDACTED]

Approved

The overall study designs for the phase 1b [redacted] parts of the study are described by the study schemas in [Section 2.1](#). The endpoints are defined in [Section 4.1](#).

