5.2 Number of Subjects

[figure not shown]
In the phase 1b part of the study sufficient subjects will be randomized to yield approximately 48 evaluable subjects (approximately 36 randomized to AMG 592 and 12 randomized to placebo; see [Section 5.2.1](#)). The total sample size may be higher than 48 subjects if, following a DLRM recommendation, additional dosing cohorts are added and/or existing cohorts are expanded, or if subjects are replaced as per [Section 5.2.1](#). Additional subjects may be enrolled in each cohort to enable all screened eligible subjects to participate in the study. Within each cohort subjects will be randomized to AMG 592 or placebo in a 3:1 ratio.

Subjects in this clinical investigation shall be referred to as “subjects”. For the sample size justification, see [Section 10.1](#).

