7.8.2.4 DMARDS

In the phase 1b part of the study only, subjects entering the study taking sulfasalazine, hydroxychloroquine, minocycline or leflunomide cannot change their dose during the initial treatment period. After the treatment period, new non-biologic DMARDs may be added or dose adjusted per investigator judgment.

Approved

8. Discontinuation Criteria

Subjects have the right to withdraw from investigational product and/or other protocol-required therapies, protocol procedures, or the study as a whole at any time and for any reason without prejudice to their future medical care by the physician or at the institution.

The investigator and/or sponsor can decide to withdraw a subject(s) from investigational product, device, and/or other protocol-required therapies, protocol procedures, or the study as a whole at any time prior to study completion for the reasons listed in [Sections 8.1, 8.2.1, and 8.2.2](#).

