10.1.1 Phase 1b

It is anticipated that approximately **48** subjects will be **randomized** in the phase 1b part of the study, with 8 subjects **randomized** to each of **cohorts 1 and 4** and **approximately 16 subjects randomized to each of cohorts 2 and 3**. The total sample size may be higher than 48 subjects if, following a DLRM recommendation, additional dosing cohorts are added and/or existing cohorts are expanded, or if subjects are replaced as per [Section 5.2.1](#). Within each cohort subjects will be randomized to **AMG 592** or placebo in a 3:1 ratio.

[figure not shown]
The sample size of the phase 1b part of the study is based on practical considerations. **For cohorts 1 and 4, with 6 subjects receiving AMG 592 in each cohort**, there is an 82% chance of at least 1 subject **within a cohort** experiencing an adverse event, if the true event rate is 25%. The chance of at least 1 subject experiencing an adverse event **within a cohort** will be 74% if the event rate becomes 20%.

For cohorts 2 and 3, with 12 subjects receiving AMG 592 in each cohort, the chance of at least 1 subject experiencing an adverse event within a cohort increases to 97% and 93% for true event rates of 25% and 20%, respectively. In addition, with a total of 36 subjects planned to receive AMG 592 in the phase 1b part of the study, the chance of at least 1 subject experiencing an adverse event across the cohorts increases to 30% and 84% if the true event rates are 1% and 5%, respectively.

Additional subjects may be enrolled at a randomization ratio of 3:1 to AMG 592 or placebo to enable all screened eligible subjects to participate in the study, for addition and/or expansion of cohorts based on DLRM recommendations, or for replacement of subjects as per [Section 5.2.1](#).

Approved

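### After a Grade 4 or higher event, Table 7-1 does not clearly hold dosing of subjects already on treatment, or of the affected subject, until the DLRM votes

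*Protocol*

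**What the plan says.** Table 7-1 has two triggers, each with an immediate step, a review and a vote.

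- **Row 1** fires on Grade 3 events judged related to investigational product in 2 or more subjects of one cohort. Its immediate step is "Stop dosing and convene DLRM (if event occurs outside the regularly scheduled DLRM".
- **Row 2** fires on a single event of Grade 4 or higher, whatever its cause. Its immediate step is "Stop dosing additional subjects in the cohort and convene DLRM (if the event occurs outside the regularly scheduled DLRM".

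In row 2 the wider stop comes later and is conditional. If a DLRM majority finds the event both related and clinically or medically significant, "no further doses should be administered at this dose and no dose escalation should proceed". Otherwise the options are worded in terms of enrollment resuming, the cohort expanding or a lower dose being used.

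Footnote a, attached in both rows to the step at which unblinding is considered, adds: "A decision to stop dosing will not occur without unblinding of the" subject's assignment.

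**The concern.** The more severe trigger has the narrower interim wording. If *additional subjects* means subjects still to be started, row 2 closes the door to newcomers and is silent about those already being injected at the dose in question. They, and the subject who had the event, could be dosed again before anyone has reviewed a possibly related Grade 4 or fatal event.

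The risk is not abstract. Section 3.2.5 reports two serious hypersensitivity reactions to AMG 592. Treatment lasts 12 weeks, and the scheduled DLRM falls after the last subject's week 4 visit, so a full cohort will normally still have subjects under treatment.

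**Working it through.** The stopping rule carries no figure of its own. The design figures in Section 10.1.1 do reproduce (for 6 subjects, 1 − 0.75^6 = 82.2% and 1 − 0.80^6 = 73.8%, stated as 82% and 74%), but nothing below depends on them. The check is mainly textual.

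**1. What the phrase means elsewhere in the protocol.**
- Section 5.1.1, on extra cohorts: "add additional subjects at previously given dose levels".
- Section 5.2: "Additional subjects may be enrolled in each cohort to enable all screened eligible subjects to participate in the study".
- Section 10.1.1: "Additional subjects may be enrolled at a randomization ratio of 3:1 to AMG 592 or placebo".

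All three concern people not yet in the trial. Row 2's own follow-on points the same way: if the event is not found related and significant, what may resume is enrollment, which suggests that enrollment is what was paused.

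**2. Whether another section supplies the hold.**
- Section 7.4.3 has withholding in its heading but states no rule for it, only that dose adjustments are not allowed.
- Section 8 gives a discretionary power: "The investigator and/or sponsor can decide to withdraw a subject(s) from investigational product". Section 8.1 lists adverse events among the reasons for removal and refers back to Section 7.4.2.
- Appendix 7 sets withholding rules, for potential hepatotoxicity only.
- SAP 7.1 describes the DLRM analyses and adds no hold.

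None requires an interim hold because a Grade 4 or higher event has occurred.

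**3. How many subjects are affected.** The planned 3:1 allocation gives 6 AMG 592 and 2 placebo in a cohort of 8, and 12 and 4 in a cohort of about 16 (cohorts 2 and 3).

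| Situation, nobody finished or discontinued | Cohort of 8 | Cohort of 16 |
|---|---|---|
| Full cohort, reached if the phrase means new subjects | 0 | 0 |
| Full cohort, reached if it means every other member | 8 − 1 = 7 | 16 − 1 = 15 |
| Others on AMG 592, event in an AMG 592 subject | 6 − 1 = 5 of 7 | 12 − 1 = 11 of 15 |
| Others on AMG 592, event in a placebo subject | 6 of 7 | 12 of 15 |

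The last two rows are upper bounds. With d other AMG 592 subjects already off treatment, the figure for a cohort of 8 becomes (5 − d) of (7 − d): 4 of 6 for d = 1, 3 of 5 for d = 2. In cohorts 2 and 3 the first 8 subjects may have finished before the second 8 start. With k of 8 subjects started, the new-subjects reading covers 8 − k: 4 when k = 4, and 0 when k = 8 (before any over-enrollment or expansion).

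**4. How long the gap lasts.** No time limit is set for an unscheduled DLRM. Appendix 3 requires more than 50% of the investigators who have enrolled a subject, and the meeting is rescheduled without a quorum. Section 5.2.2 plans about 18 sites. With the dosing interval redacted, the number of doses given before a vote cannot be computed.

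**5. What a hold would cost in doses.** Section 7.1.1.1.1 says that after week 4 (week 12 excepted) a dose outside its ±1 day window is skipped. From day 1 to day 85 there would be 84/7 + 1 = 13 doses if weekly, or 84/14 + 1 = 7 if every 2 weeks; both intervals are assumptions. A hold of up to 7 days contains at most 1 scheduled dose in either case.

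**The case against.** The best defence is that *additional* may mean every other subject due a dose. The verb in row 2 is dosing, its object is subjects in the cohort, and the table says enrollment elsewhere when it means intake. In the sections cited above, the sense of newness comes partly from verbs such as add and enroll. The lead-in to Table 7-1 also speaks of dosing being stopped or modified. This stands as a possible reading. It does not settle the matter, and it leaves the affected subject unmentioned.

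It is also fair that the rows are not like for like. Row 2 fires on one event of any cause, so a narrower first step could be deliberate. A reader might infer that row 2 is the laxer rule overall. It is not: a related and significant event ends dosing at that dose and bars escalation. The weakness is confined to the interim step.

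There are practical safeguards. The investigator or sponsor may withdraw a subject, an unblinded sponsor lead monitors the study (Section 7.3.2), and the sponsor may stop the study or a site for safety reasons (Appendix 3). These reduce the practical risk, but all are discretionary.

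Two further inferences go too far:
- That the protocol never requires treatment to stop outside the hepatotoxicity rules. Row 1 does, and so do pregnancy and breastfeeding (Appendix 5). The gap concerns Grade 4 or higher events only.
- That footnote a forbids an immediate hold until the subject is unblinded. Its marker sits at the review step, after the immediate action, so it most plausibly governs the DLRM's decision. It adds minor doubt, because it does not separate a temporary hold from a final stop.

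**Conclusion.** The point holds as a missing or ambiguous hold. On the more natural reading, row 2's interim step does not reach subjects already on treatment. On the other reading it reaches all of them except the affected subject, whose dosing is still not addressed. A reader might infer that the table tells sites to go on dosing; it does not say that, and a cautious site would probably stop. But a first-line instruction after a possibly fatal event should not depend on which reading a site adopts.

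The size is 0 against 7 subjects reached in a full cohort of 8 (0 against 15 in a cohort of 16), assuming everyone is still on treatment and there is no over-enrollment. These are counts of subjects covered, not of doses given or harm caused. Sample size and analyses are unaffected. Confidence is moderate, because the conclusion rests on the ordinary meaning of one phrase. The change is worth making because it is cheap and concerns subject safety.

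**What to change.** Reword the first step of row 2 so that dosing stops for all subjects in the cohort, including the affected subject, and leave the requirement to convene the DLRM as it is. As a minor clarification, state in footnote a that the unblinding condition applies to the DLRM's decision to stop dosing and not to the immediate hold in either row.

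An exception for events judged clearly unrelated is tempting as a way to save doses. It would need a named judge and a standard, and it could loosen a rule that now applies whatever the cause. The plain wording is better.

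The cost is a protocol amendment of one sentence and one footnote, plus the doses that fall within a hold: at most 1 per subject if the hold lasts up to a week and dosing is weekly or less often, and more if the DLRM is delayed. That means a small loss of exposure and PK data, which matters somewhat here because Amendment 3 expanded cohorts 2 and 3 after early drop-outs left those data insufficient.
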